 8. Brief Resiliency Score (BRS): Range 1 (low resilience) – 5 (high resilience); MDC = Δ low (1-2.99) to normal (3-4.3) to high (4.31-5)
 9. ACL-RSI: Range 1 (low function) – 100 (high function); MDC = Δ 15.1 for short form version
 10. IKDC : Range 1 (low function) – 100 (high function); MDC = Δ 8.8 low to Δ 15.6 high
 11. All PROs are nationally validated measures.
- b. Description of Population to be Studied:
 - i. General: patients aged 16-60 years old with knee joint pain to be treated operatively with knee arthroscopy. Based off the power analysis for both knee extensor strength and Tegner, we will recruit at least 78 participants (39 per group).
 - ii. Timeframe: BFR protocol administered 0-12 weeks post operatively, but data will be collected up until 2 years post operatively. Patients may be consented at pre-op or will be consented in person before or during their first post-operative physical therapy appointment. After being consented, subjects will be contacted via email and/or text message to prompt survey completion.
 1. PRO's will be collected at:
 - a. Initial evaluation

- i. Form is sent 7 days before surgery with an 8-day window for completion
- b. 3 weeks
 - i. Form is sent 3 weeks after surgery with a 7-day window for completion
- c. 6 weeks
 - i. Form is sent 6 weeks after surgery with a 7-day window for completion
- d. 12 weeks
 - i. Form is sent 10 weeks after surgery with a 30-day window for completion
- e. 6 months
 - i. Form is sent 24 weeks after surgery with a 30-day window for completion
- f. 9 months
 - i. Form is sent 36 weeks after surgery with a 30-day window for completion
- g. 1 year
 - i. Form sent 365 days after surgery with a 30-day window for completion
- h. 2 years
 - i. Form sent 730 days after surgery with a 30-day window for completion

2. Strength, ROM and functional performance measurements will be collected at 6 weeks, 12 weeks, 6 months and at discharge.

- iii. Inclusion criteria: Patients with ACL reconstruction with quadriceps, hamstring, bone-patellar-bone or allograft graft, with/without meniscectomies. Patients must also have access to a smartphone device in order to utilize the SAGA BFR application for use. The application is free to use.

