 - ii. Secondary measures will be collected through PatientIQ platform for patient reported outcome measures including: Tegner, LEFS, pain and resiliency scores. Data will be collected via Patient IQ and electronically stored within the platform. Platform is HIPAA compliant, and password protected. PatientIQ is routinely used by Orthopedics clinically and for research, and is approved by CU Medicine and UCHHealth.
- d. Potential Scientific Problems
- i. Lack of compliance with BFR protocol, lack of compliance with general post-operative standards/restrictions, subjects lost to follow up, poor exercise technique/performance, difficulty with application and/or device malfunction, pain while using device
- e. Data Analysis Plan:

General Statistical Considerations:

All analyses will assume a two-sided test of hypothesis, $\alpha=0.05$, and be run in SAS v9.4 (Cary, NC) or higher or R v4.1.1 or higher. Randomization will be checked by comparing baseline demographic and clinical characteristics between groups using t-tests, chi-square tests, Wilcoxon rank-sum or Fisher's exact tests, as applicable. Preliminary descriptive and graphical analyses (e.g., boxplots, scatterplots, and profile plots over time) will be used to check and visualize data. Transformations for outcome measures will be considered as necessary

- i. The primary analysis:
 - 1. Analysis will be an intent-to-treat (ITT) comparison of the differences between treatment groups in strength at the primary endpoint of 3 months. No interim analyses are planned. Statistical inference regarding the difference between treatment groups will be based on a restricted maximum likelihood linear mixed model including all time points with strength at 3 months as the response variable and group assignment as

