the primary independent variable. Covariates will include sex (stratification variable) and additional covariates will be considered if group differences at baseline are identified for any demographic or clinical characteristic that is a plausible confounder. The conclusion about differences between treatment groups will be determined by this single statistical test to protect against an elevated risk of false positive conclusions. Measures at other time points (3 weeks, 6 weeks, 12 weeks, 6 months, 12 months & 24 months) will be evaluated using a restricted maximum likelihood, repeated-measures linear mixed-model including all time points, with linear contrasts to estimate within and between group differences over time. We anticipate that secondary timepoints will be correlated with the primary timepoint, so that similar effects on secondary time points will reinforce significant differences in the primary outcome/time point.

ii. Secondary Analyses:

1. Secondary outcomes at primary endpoint of 3 months will be analyzed as described above. Secondary outcomes will be evaluated for their consistency with the primary outcome. We anticipate that secondary outcomes will be correlated with the primary, so that similar effects on secondary outcomes will reinforce significant differences in the primary outcome. Failure to observe consistency between primary and secondary outcomes will be taken as evidence that the effects of blood flow restriction training are not clear, and that further study is necessary to resolve inconsistencies. This approach reduces the risk of false-positive conclusions resulting from multiple statistical tests. Measures at other time points will be evaluated using a restricted maximum likelihood, repeated-measures linear-mixed model with linear contrasts to estimate within and between group differences in change over time. Sensitivity to non-compliance with BFR (<80% of prescribed sessions) and attendance at PT sessions (<80% attendance) will also be evaluated in secondary analyses; that is, a per-protocol analysis will be compared to the ITT results.

iii. Power

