Appendix I: Standard Protocol for Knee Arthroscopy, ACL Reconstruction

	Approximate Time Frame (Weeks)	Activity	Goals
PHASE I	0-2	
WB Status: PWB 50%*
 
Brace: 0-90 x 6 weeks
 
ROM: 0-120+*
 
Manual: patella mobilization, gentle STM to reduce edema, soreness, stiffness above/below knee PRN
 
Exercise:
 
 • Quad sets (w/NMES PRN) • P/AA range of motion exercises • Multiplane SLR/OKC hip w/knee straight • Calf raises/ankle strengthening 
Cardiovascular: Begin stationary bike when ROM allows
	
 ◇ Extension to 0 ◇ SLR no lag ◇ Control inflammation ◇ Minimize DVT risk ◇ 100-120+ flexion ◇ Normalize PF mobility ◇ Normalize gait with crutches
PHASE II	2-6	
WB: FWBAT no limp
 
Brace: continue 0-90 until week 6
 
ROM: full
 
Manual: STM/MFR PRN, scar mobilization once healed. Patella mobs 0/30. Aggressive patella/anterior interval mobilization on BTB grafts
 
Exercise progression:
 
 • CKC double leg -> single leg progression • Concentric and eccentric considerations • Hip/core/calf strengthening • Proprioception • Hamstring strength-no ham curl w/external load for hamstring autograft • LE stretching w/consideration for harvest site 
Cardiovascular: Stationary bike w/resistance Short walks, Alter-G Deep pool running at week 4 and incisions fully healed
	
 ◇ normalize gait ◇ Minimize swelling, PF pain ◇ Full ROM; extension equal to opposite side ◇ Muscular endurance progressing into strength ◇ Proper squat pattern; perform on two legs with good control, equal WB before progressing to single leg

	Approximate Time Frame (Weeks)	Activity	Goals

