PHASE III	6-12	
Manual: PRN to address ROM deficits/PF pain. Mobilize scars (BTB graft)
 
Exercise progression:
 
 • Independent myofascial management (FR, massage stick, ball) • Controlled movement series • CKC PRE's bilateral & unilateral , emphasizing single leg strength • Advance core program/accessory hip muscles • Hamstring grafts: gradually add resistance to knee flexion 8-10 wks 
Cardiovascular:
 
 • Swimming, shallow pool running, elliptical 6 weeks • Outdoor biking 8-10 weeks • Interval CV work, Alter-G running 10-12 weeks 
Running/Agility: Basic linear ladder drills week 10
	
 ◇ Minimal to no PF pain as strength training advances ◇ Full terminal motion ◇ No effusion ◇ 75% LSI of quads, hams ◇ Single leg squat x 90 to at least 30 degrees With 75% LSI 
Must meet goals in order to begin running

PHASE IVa	3-6 mos	
Strengthening:
 
 • Advance PRE's of hip, knee, ankle • Incorporate power into training, considering individual need 
Cardiovascular: High intensity low impact cardio to build fitness, lower intensity cardio for recovery and Alter-G for progressive loading. Impact starting 2-3 days/week
 
Running Progression:
 
 • Basic ladder/linear drills with gradual advancement of difficulty • Walk/jog interval -3 months • Linear acceleration/deceleration-4months • Sprinting, cutting, lateral agility-5 months (gradually increase intensity) 
Jumping: single response progressing to multiple response jumps
 
 • Double leg, low amplitude jumps starting 3-4 months • Progressing to single leg hop 4-5 months 	
 ◇ Manual therapy only PRN to address terminal motion deficit and/or pain ◇ Control inflammation with increasing loads/impact ◇ Limb symmetry with all strength exercises ◇ Normalize running gait ◇ Y test <4cm difference ◇ Lateral dip x 1 minute with 90% LSI ◇ IKDC > 7/10

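### Covariates beyond sex depend on observed baseline imbalance, so the decisive model is not fixed in advance and graft source will usually be left out

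*Protocol*

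**What the plan says.** Section 5.e.i (The primary analysis) names sex, the stratification variable, as a covariate. For anything else the rule is that "additional covariates will be considered if group differences at baseline are identified for any demographic or clinical characteristic that is a plausible confounder". No candidate variables are listed and no threshold is given.

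Section 5.e (General Statistical Considerations) says how differences are looked for: "Randomization will be checked by comparing baseline demographic and clinical characteristics between groups using t-tests" and the corresponding categorical and rank tests.

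Section 5.e.i also states: "The conclusion about differences between treatment groups will be determined by this single statistical test", and gives protection against false positives as the reason.

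Section 4.b.iii admits "Patients with ACL reconstruction with quadriceps, hamstring, bone-patellar-bone or allograft graft, with/without meniscectomies". Section 4.c.ii controls randomisation for sex only. On strength, section 4.b.ii says "Strength, ROM and functional performance measurements will be collected at 6 weeks, 12 weeks, 6 months and at discharge", and the schedule table in section 4.c lists no measurements before surgery.

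For the other outcomes, section 5.e.ii says: "Secondary outcomes at primary endpoint of 3 months will be analyzed as described above".

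**The concern.** Adjustment in a randomised trial is justified by how strongly a variable predicts the outcome, not by whether the arms happen to differ on it. A rule triggered by baseline tests therefore works on the wrong quantity: it ignores a strong predictor that looks balanced and may admit a weak one that does not. It also leaves the content of the decisive model unknown until baseline data have been compared by arm, and the word considered leaves the final choice to judgement. That sits badly with resting the conclusion on one test.

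Graft source is where this matters most on the protocol's own content:

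- It is known for every patient, and randomisation does not control it.
- Quadriceps and bone-patellar-bone grafts come from the extensor mechanism, and knee extensor limb symmetry is the primary endpoint.
- For hamstring grafts, Appendix I limits loaded knee flexion in Phase II ("no ham curl w/external load for hamstring autograft") and in Phase III has patients "gradually add resistance to knee flexion 8-10 wks". Flexor strength, a secondary outcome, is then measured at 12 weeks.
- Strength has no pre-operative value, so no baseline strength covariate can supply the precision instead.

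The patient-reported outcomes inherit the rule. They do have a pre-operative score, but the model is described as using every visit while having the 3-month value as its response. The text does not settle whether, or how, that score enters.

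At stake are precision, protection against a chance graft imbalance in one small trial, and a model that is known in advance.

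**Working it through.** **The plan's own figure.** Section 5.e.iii gives 11 ± 13 against 3 ± 9. The pooled SD is √((13² + 9²)/2) = 11.18, so d = 8/11.18 = 0.716 (stated as 0.72). A two-sided t-test at 0.05 with 80% power needs 31.3 (d = 0.72) to 31.6 (d = 0.716) per arm. That rounds to 32 per arm, 64 in total, as stated. At 32 per arm and d = 0.72, power is 80.9%.

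**How often the rule lets a variable in.** A valid test at 0.05 flags a given baseline variable in about 5% of randomisations. In simulation a chi-square test on graft fired in 5.3% of trials, so graft is left out in about 95%. The chance that at least one of k independent variables is flagged is 1 − 0.95^k: 14% for k = 3, 23% for k = 5 and 40% for k = 10. Whether the model gains a covariate is therefore partly a lottery.

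**What fixing graft source would do to power.** Assumptions: 32 per arm, d = 0.716, sex in every model, graft in three levels with shares 50/25/25%, trigger p<0.05, and 40,000 simulated trials. R² is the share of outcome variance explained by graft; the protocol gives no value, so a range is shown.

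| R² | Power, graft never in (%) | Power, stated rule (%) | Power, graft always in (%) | CI width, always / never |
|---|---|---|---|---|
| 0 | 80.8 | 80.5 | 79.4 | 1.018 |
| 0.02 | 80.8 | 80.6 | 80.2 | 1.008 |
| 0.05 | 80.8 | 80.8 | 81.4 | 0.992 |
| 0.10 | 80.7 | 80.8 | 83.4 | 0.966 |
| 0.16 | 80.6 | 81.0 | 85.8 | 0.933 |
| 0.25 | 80.6 | 81.3 | 89.3 | 0.881 |

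The rule performs almost exactly like never adjusting. With no treatment effect, type I error is 4.6–5.1% under the rule and 5.1% with graft always in.

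**Sensitivity to the grouping.** A separate simulation used all four graft types with assumed shares 30/20/35/15%, d = 0.72 and 10,000 trials per scenario. Power under the rule against fixed adjustment was 80.7% vs 82.7% at R² 0.10, 81.0% vs 87.1% at 0.20 and 80.9% vs 91.2% at 0.30. The pattern is the same. In that simulation type I error under the rule was 4.5–4.7%. It reached 6.3–7.5% only if an analyst could pick the better of the adjusted and unadjusted results.

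**What a chance graft imbalance does in one trial.** For a graft type with a 50% share, the SD of the difference in proportions between arms is √(2 × 0.25/32) = 0.125, which is 12.5 percentage points or 4 of 32 patients. A gap at least that large occurs in 38% of trials, and 89% of those are not flagged at p<0.05. If that type differs from the rest, a one-SD gap moves the unadjusted estimate by 2 × √R² × 0.125:

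- R² 0.02: 0.035 SD, and 0.035/0.716 = 5% of the planned effect
- R² 0.10: 0.079 SD, 11%
- R² 0.25: 0.125 SD, 17%

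The sign of the shift is random. This describes the same lost precision as the table, seen from within a single trial; it is not an additional loss.

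**The case against.** The strongest reply is that nothing is broken. Applied mechanically, the rule keeps type I error near 5% and power at the planned 80%, and the unadjusted estimate is unbiased over repeated randomisations. This stands. The higher error rates need an analyst choosing between results, which the protocol does not describe. Only baseline data trigger the rule, and nothing says that outcomes inform it.

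The gain rests on an R² that the protocol does not state. This also stands: below about 0.05 there is no material benefit, and at zero there is a cost of about 1 point. The case that graft predicts extensor strength is anatomical; the graft-specific limits cited from Appendix I concern knee flexion, which is secondary. Choosing graft over, say, age or meniscectomy is a judgement.

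The 95% and 89% figures depend on reading the trigger as p<0.05. The protocol's general alpha makes that reasonable, but a visible gap could be called a difference without reaching it.

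Finally, candidate lists and thresholds, like the handling of pre-operative patient-reported scores, are often left to a statistical analysis plan. That would answer mere silence. Here the protocol itself lays down that imbalance decides, and a later plan that followed it would inherit the fault. No other part of the protocol removes the rule.

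**Conclusion.** The concern holds, as an improvement that should be made rather than an error that invalidates the test. The protocol makes every covariate except sex conditional on chance baseline differences, so the content of its one decisive model is not known in advance and graft source would be omitted in about 95% of randomisations at a p<0.05 trigger. Against the stated rule, always including graft costs about 1 point of power if graft is irrelevant, changes little up to R² 0.05, and gains about 3 to 8 points at R² 0.10–0.25. These figures assume 32 evaluable patients per arm, the protocol's effect size carried over to the limb symmetry endpoint, the graft shares shown and a p<0.05 trigger. Confidence in the size is moderate, because the protocol gives no R² for graft; the fault in the rule does not depend on that value.

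**What to change.** Replace the conditional rule in section 5.e.i with a fixed covariate set, used whatever the observed balance:

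- **Strength and single-leg squat outcomes:** sex and graft source, with the grouping stated in advance, for example quadriceps or bone-patellar-bone, hamstring, allograft.
- **Each patient-reported outcome:** the same two plus its pre-operative score, either as a covariate or through a mixed model with a common baseline mean for the two arms.

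In section 5.e, keep the description of baseline characteristics by arm but do not use tests to choose covariates.

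The cost is analysis wording only, on data already collected. Graft takes two degrees of freedom and a pre-operative score one more, out of about 60 (64 patients less intercept, arm and sex leaves 61). The downside is about 1 point of power if graft source turns out not to predict the outcome.

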Appendix I: Standard Protocol for Knee Arthroscopy, ACL Reconstruction

	Approximate Time Frame (Weeks)	Activity	Goals
PHASE I	0-2	
WB Status: PWB 50%*
 
Brace: 0-90 x 6 weeks
 
ROM: 0-120+*
 
Manual: patella mobilization, gentle STM to reduce edema, soreness, stiffness above/below knee PRN
 
Exercise:
 
 • Quad sets (w/NMES PRN) • P/AA range of motion exercises • Multiplane SLR/OKC hip w/knee straight • Calf raises/ankle strengthening 
Cardiovascular: Begin stationary bike when ROM allows
	
 ◇ Extension to 0 ◇ SLR no lag ◇ Control inflammation ◇ Minimize DVT risk ◇ 100-120+ flexion ◇ Normalize PF mobility ◇ Normalize gait with crutches
PHASE II	2-6	
WB: FWBAT no limp
 
Brace: continue 0-90 until week 6
 
ROM: full
 
Manual: STM/MFR PRN, scar mobilization once healed. Patella mobs 0/30. Aggressive patella/anterior interval mobilization on BTB grafts
 
Exercise progression:
 
 • CKC double leg -> single leg progression • Concentric and eccentric considerations • Hip/core/calf strengthening • Proprioception • Hamstring strength-no ham curl w/external load for hamstring autograft • LE stretching w/consideration for harvest site 
Cardiovascular: Stationary bike w/resistance Short walks, Alter-G Deep pool running at week 4 and incisions fully healed
	
 ◇ normalize gait ◇ Minimize swelling, PF pain ◇ Full ROM; extension equal to opposite side ◇ Muscular endurance progressing into strength ◇ Proper squat pattern; perform on two legs with good control, equal WB before progressing to single leg

	Approximate Time Frame (Weeks)	Activity	Goals
PHASE III	6-12	
Manual: PRN to address ROM deficits/PF pain. Mobilize scars (BTB graft)
 
Exercise progression:
 
 • Independent myofascial management (FR, massage stick, ball) • Controlled movement series • CKC PRE's bilateral & unilateral , emphasizing single leg strength • Advance core program/accessory hip muscles • Hamstring grafts: gradually add resistance to knee flexion 8-10 wks 
Cardiovascular:
 
 • Swimming, shallow pool running, elliptical 6 weeks • Outdoor biking 8-10 weeks • Interval CV work, Alter-G running 10-12 weeks 
Running/Agility: Basic linear ladder drills week 10
	
 ◇ Minimal to no PF pain as strength training advances ◇ Full terminal motion ◇ No effusion ◇ 75% LSI of quads, hams ◇ Single leg squat x 90 to at least 30 degrees With 75% LSI 
Must meet goals in order to begin running

PHASE IVa	3-6 mos	
Strengthening:
 
 • Advance PRE's of hip, knee, ankle • Incorporate power into training, considering individual need 
Cardiovascular: High intensity low impact cardio to build fitness, lower intensity cardio for recovery and Alter-G for progressive loading. Impact starting 2-3 days/week
 
Running Progression:
 
 • Basic ladder/linear drills with gradual advancement of difficulty • Walk/jog interval -3 months • Linear acceleration/deceleration-4months • Sprinting, cutting, lateral agility-5 months (gradually increase intensity) 
Jumping: single response progressing to multiple response jumps
 
 • Double leg, low amplitude jumps starting 3-4 months • Progressing to single leg hop 4-5 months 	
 ◇ Manual therapy only PRN to address terminal motion deficit and/or pain ◇ Control inflammation with increasing loads/impact ◇ Limb symmetry with all strength exercises ◇ Normalize running gait ◇ Y test <4cm difference ◇ Lateral dip x 1 minute with 90% LSI ◇ IKDC > 7/10
PHASE IVb	5-9 mos	
Focus shifted to impact and sports specific activities
 
Strength:
 
 • Weight training volume is maintaining or decreasing, continue to increase resistance as tolerated 2-3x/week • Perform strength training after running/agility OR on opposite days 
Plyometrics
 
 • Progress based on sport demands, individual ability 
RTS progression: (see specific sport protocol for details)
 
 • Unidirectional agility drills, progressing to multidirectional • Begin position and sport specific skills-drills • Non-reactive progressing to reactive drills-coach or PT directed 
Practice/game progression, after passing sports test:
 
 ⇒ Participation in all practice drills ⇒ Scrimmage participation with no contact ⇒ Scrimmage or game situation with contact, limited playing time ⇒ Return to sport with increasing game minutes 	
 ◇ Reconditioning for sport demands ◇ Correct faulty movement with high level tasks ◇ Emphasize both limbs for injury prevention ◇ RTS test @ 6+ months ◇ IKDC > 9/10 ◇ Return to practice with gradual progression to game play 
RTS test may be modified per therapist's discretion based on patient demographics and goals

